7.3. Cognitive interviewing visit

An interviewer, who will receive training in cognitive interviewing, will guide participants through orientation to the workbook and using the wearable device, mobile app, and photo printer at this initial meeting. Interviews one week later will use a combination of think-aloud and probing procedures from a semi-structured guide, as has been used in development of other behavioral interventions.³⁴⁻³⁶

- Collect and document returned materials
- Prepare audio recorder
- Administer Aim 1 Cognitive Interviewing checklist and guide
- Provide participant gift card and document

8. STUDY SCHEDULE - RCT

During the COVID-19 pandemic, the following consenting/interview methods will be implemented:

In response to the COVID-19 pandemic and related Institutional guidelines, the following modifications are being implemented effective immediately:

All visits will be conducted entirely by teleconference call. Ongoing participants will receive a phone call by study staff to inform the subject of the implemented modifications. We will read the modification letter to the subject over the phone. If the subject agrees with the modifications, we will document the subject verbal response in a note to file. If we are not able to reach the subject, we will mail the subject a letter.

8.1. Screening

We have collaborated with oncologists at various clinics to expand our effort in recruitment. A HIPAA waiver request form has been completed. With the oncologist's approval, we will pre-screen patients via medical records for eligibility. The oncologists will refer their patients. We will not approach UTMB patients unless we have oncologist's and patient's permission.

For patients at MD Anderson clinics, as discussed above in section x, staff will review upcoming patient appointments in the clinic via EPIC and call potentially eligible participants. Whereas at UTMB we must obtain practitioner permission to approach patients, all MD Anderson patients have provided consent to be approached by research-related phone calls and emails. If the patient is interested and eligible, UTMB study staff will later call to set up an appointment for informed consent, baseline assessment, and randomization/study orientation.

Research staff will use the RCT screening guide, either in person or by phone, to determine eligibility in the study. Should the participant be found eligible, the staff member will schedule an appointment for informed consent and enrollment.

8.2. Enrollment and provision of accelerometer

Research staff will conduct the informed consent interview. Once the interview is complete and participants have asked any questions they may have, the participant and staff member will each sign two copies of the consent form. One copy will be provided to the participant and the other kept for study records. The staff member will take the participant's height, weight and waist circumference at this visit and ask several demographic questions (age, gender, race) for the purposes of calibrating the accelerometer. Once calibrated and activated, the staff member will provide instructions as to wearing the accelerometer for one week. At the conclusion of this visit, the staff member will schedule a follow-up appointment for approximately one week after the enrollment appointment.

- Obtain and document consent from participant on study consent form
- Obtain height, weight and waist circumference measurements
- Calibrate and activate accelerometer

COVID-19 adjustments for consenting/enrollment:

- The visit will be conducted using teleconference communication (examples: via phone, skype, zoom)
- Consent will be obtained via teleconference call and the study subjects will scan or photograph and transmit the signed consent form to us via email or text.

- Height, weight, and waist measurements- we will obtain self-reported height, weight, and waist measurements. If possible, we will obtain measurements at a future face to face visit if available.
- We will drop off and pick up the activity monitor. For the participant to wear for 7 days, for at least 10 hours per day.
- We will give the option to participants to complete an assessment visit when the recommended guidelines are lifted, and we are able to have a face to face visit.
- We will give participants paper forms of the questionnaires to complete prior to the baseline visit.

8.3. Baseline and orientation visit

Participants will return after approximately one week to engage in baseline assessment, be randomized to a condition, and to begin the intervention. Baseline assessments will include height, weight and waist circumference, collection of the accelerometer and questionnaires. A staff member will randomize the participant and then, based on their condition, provide them with appropriate materials. The staff member will go over these materials in detail, following a specific checklist. S/he will also check off materials provided on a separate log sheet. Participants will engage in a brief goal-setting activity before leaving.

- Collect and document accelerometer
- Check accelerometer data to ensure that they include at least 10 hours on at least 4 days
- *If not enough days are found, request that participant wear an accelerometer for an additional 7 days and return for their randomization afterwards
- Administer questionnaires
- Randomize participant

For the narrative visualization intervention:

- Follow RCT visit 2 checklist to document each step
- Provide activity monitor
- Download activity monitor app onto participant's mobile device and provide orientation
- Provide workbook
- Orient participant to contents of the workbook
- Provide camera, film, writing materials, stickers, photo corners, film, and bag and provide orientation
- Administer goal-setting activity

For the self-monitoring only intervention:

- Follow RCT visit 2 checklist to document each step
- Provide activity monitor
- Download activity monitor app onto participant's mobile device and provide orientation
- Provide workbook
- Orient participant to contents of the workbook
- Provide writing materials
- Administer goal-setting activity

COVID-19 adjustments for baseline/orientation:

- The initial portion of the visit will occur in-person. Study staff will wear personal protective equipment and follow safety precautions, such as sanitizing equipment. The in-person portion will consist of obtaining measurements, retrieving the activity monitor, providing participant materials, and assisting with downloading the Fitbit app onto participant phones.
- The rest of the orientation portion of the visit will be conducted using teleconference communication (examples: via phone, skype, zoom)

8.4. 12 week follow-up

After approximately 10 weeks, a staff member will document and mail the participant a calibrated accelerometer and questionnaires. The staff member will call the participant to ensure receipt and to make sure it is fitted correctly. At approximately 12 weeks, the participant will meet with an assessor to measure height, weight, waist circumference and collect the accelerometer and questionnaires. A brief interview will also occur. Study staff will follow a guide with a checklist to ensure the interview proceeds as planned.

- Mail accelerometer and questionnaires (approximately 2 weeks before), call to inform participant, and document.
- Phone/email/text reminder to bring workbook to appointment (day before)
- Collect accelerometer
- Check accelerometer data to ensure that they include at least 10 hours on at least 4 days
- *If not enough days are found, request that participant wear an accelerometer for an additional 7 days and return it in a provided padded, pre-stamped envelope
- Administer or collect questionnaires
- Make copies/take pictures of workbook pages
- Conduct interview according to RCT interview guide and checklist
- Provide gift card and document

COVID-19 adjustments for consenting/enrollment:

- We will collect the activity monitor and questionnaires during a brief in-person visit. Study staff will wear personal protective equipment and sanitize equipment as needed. The gift card will be provided at the conclusion of this visit.

8.5. 24 week follow-up

After approximately 22 weeks, a staff member will mail the participant a calibrated accelerometer and possibly questionnaires. The staff member will call the participant to ensure receipt and to make sure it is fitted correctly. At approximately 24 weeks, the participant will meet with an assessor to measure height, weight, waist circumference, collect the accelerometer, and administer or collect questionnaires.

- Mail accelerometer and possibly questionnaires (approximately 2 weeks before), call to confirm receipt, and document
- Phone/email/text reminding participant to bring the workbook to appointment (day before)
- Collect accelerometer
- Check accelerometer data to ensure that they include at least 10 hours on at least 4 days
- *If not enough days are found, request that participant wear an accelerometer for an additional 7 days and return it in a provided padded, pre-stamped envelope
- Administer or collect questionnaires
- Make copies/take pictures of workbook pages
- Provide gift card and document

COVID-19 adjustments for consenting/enrollment:

- We will collect the activity monitor and questionnaires during a brief in-person visit. Study staff will wear personal protective equipment and sanitize equipment as needed. The gift card will be provided at the conclusion of this visit.
- While reviewing data in January of 2021, we noticed that many follow-up assessments scheduled after March of 2020 were missing. We suspect many of these missing visits were due to COVID-19 in some form and wish to investigate and gather as much information as possible from these participants. Thus, we are amending our procedures for follow-up to include the possibility of contacting participants more than one month after their indicated follow-up time. These visits will be amended to consist only of questionnaire, interview, and if possible collection/photography of materials. We have added several questions about COVID-19 to our interview guide to find out more about whether or not participants used intervention materials during the pandemic. The consent form has been updated to include these procedures. When we contact participants with no follow-up data, we will conduct a new consent interview and re-consent them using the new form to ensure that they are fully aware of the updated procedures.

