3. SPECIFIC AIMS AND OUTCOMES

3.1. SPECIFIC AIMS

Aim 1. Develop and refine reflection materials among a sample of sedentary breast cancer survivors.

Aim 2. Conduct a pilot randomized controlled trial comparing the self-monitoring + narrative visualization intervention to standard self-monitoring.

- **2a.** Determine the feasibility and acceptability of intervention procedures and materials.
- **2b.** Compare the effects of the interventions on objectively-assessed PA and psychological outcomes at 12 and 24 weeks.

3.2. Primary outcomes will be feasibility and acceptability. Specifically, indicators of feasibility and acceptability will include:

- **Attrition** per intervention condition as measured by study records
- **Adherence** to wear of the activity monitor as measured by daily step information in the Fitbit app
- **Adherence** to use of the workbook as measured by observation of photographs of each workbook page (number of photographs taken for values clarification activity, completion of written portion of values clarification activity, number of days with written entries, number of days with graphic entries, photos pasted into workbook, number of stickers pasted into workbook, number of additional drawings, number of “tag” annotations added to graphs, coded level of reflection of written entries)
- **Dose delivered** as measured by study logs of materials provision
- **Dose received** as measured by self-report
- **Adverse events** as measured by self-report and study records
- **Acceptability** will be measured using quantitative items in the 12 week and 24 week questionnaires as well as in the brief interview during the 12 week assessment

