8.6. Additional communications with participants by phone, email/text, and in person

Study staff will ensure that participants have contact information for the research team and knows how to call after hours in the case of a question or problem.

Participants will be asked (but may decline) to provide alternative contacts to the study staff. At each study visit, participants will be asked if there have been any changes in their contact information or that of their alternative contacts.

Attempts at contact will be documented in each participants' contact log. Information discussed, provided to, or obtained from the participant will be documented in the log.

Study staff will provide basic technical troubleshooting with study devices (Fitbit monitor, app, camera) during business hours by text or phone. If necessary, we will set up one meeting per participant to replace broken or lost equipment. We will allow one other meeting for technical support of other kinds, if necessary.

Study staff will contact participants by phone, text or email the day before each appointment. If emailed or text regarding the appointment and scheduling, staff will respond. Study staff will also send generic cards at approximately 5 months in to the intervention period to remind the participants of their participation in the study and that they will be contacted to schedule another appointment at a later date.

Prior to determining that a participant is lost to follow up form, we will attempt to contact the participant at least 3 times, attempt contacting the alternative contact(s), and attempt a final contact by mail. A form documenting all mailed correspondence will be stored in the participants' file.

Participants will be notified that study staff may not respond to non-emergency contacts outside of normal business hours.

Additional contact may occur for the purposes of picking up/dropping off accelerometers or questionnaires.

Due to difficulties from COVID19 additional contact may occur for the purpose of collecting final questionnaires, interview, and collection/photography of material. The following steps will take place if we contact a subject for this purpose:

We will ask for their permission to re-consent for the purpose of collection/photography of material, questionnaires, and interview. This visit may be completed by using a teleconference call or in person.

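### Does the open-ended late follow-up allowed after January 2021 leave attrition, acceptability and the 12- and 24-week values undefined?

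*Combined protocol and SAP*

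**What the plan says.** Section 8.5 (24 week follow-up, COVID-19 adjustments) reports that a data review in January 2021 found that "many follow-up assessments scheduled after March of 2020 were missing". It then states that "we are amending our procedures for follow-up to include the possibility of contacting participants more than one month after their indicated follow-up time". The content of these contacts is reduced: "These visits will be amended to consist only of questionnaire, interview, and if possible collection/photography of materials". It adds: "When we contact participants with no follow-up data, we will conduct a new consent interview". Section 8.6 repeats the permission, saying that "additional contact may occur for the purpose of collecting final questionnaires, interview, and collection/photography of material". It also contains the only written rule on loss: "Prior to determining that a participant is lost to follow up form, we will attempt to contact the participant at least 3 times", followed by alternative contacts and a letter.

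Section 3.2 makes attrition a primary outcome, "per intervention condition as measured by study records", and says that acceptability "will be measured using quantitative items in the 12 week and 24 week questionnaires", with the 12-week interview in addition. Section 10.1 predicts equal attrition in the two groups, a rating above 4 out of 5 for the materials, and effects on activity and psychological measures at 12 weeks. Section 10.2 requires at least a small difference in integrated regulation before moving on and names no time point. Section 10.3.2 limits feasibility and acceptability to descriptive statistics, uses ANCOVA for the other outcomes, follows intent to treat with imputation as needed, and blinds the statistician to allocation. It does not mention late forms.

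**The concern.** The amendment changed how data are collected but added no rule for counting them. Section 8.6 defines loss by failed contact attempts without a time limit. Read literally, a woman who missed both scheduled visits and answers the telephone in 2021 is not lost, although the scheduled visits produced no data from her. Study records could therefore support two attrition figures for the same arm, and the comparison between arms could differ under the two.

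The same doubt attaches to questionnaires. A form completed months late carries acceptability items and the integrated-regulation scale, but no week label. If it is read as a 12-week value, it could enter the comparison behind the progression condition. The Summary says the results will be used to develop a follow-up study, so a flattering retention figure or a misplaced effect estimate could carry forward.

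**Working it through.** The plan gives no figure on this point and no count of late contacts. Its only sample-size figure, 80% power for 40 participants at an effect of about 0.45, does reproduce: noncentral F with noncentrality 40 × 0.45², two covariates and an assumed two-sided 5% level gives 79.1%. It is context only, since section 10.2 says significance will not be interpreted.

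**1. How late.** Assume contact between 1 and 31 January 2021. Study week = scheduled week + days late / 7.

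| Visit due | Days late | Week, if due at 12 | Week, if due at 24 |
|---|---|---|---|
| 1 Apr 2020 | 275–305 | 51.3–55.6 | 63.3–67.6 |
| 1 Aug 2020 | 153–183 | 33.9–38.1 | 45.9–50.1 |
| 1 Dec 2020 | 31–61 | 16.4–20.7 | 28.4–32.7 |

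For example, 275 / 7 = 39.3, and 12 + 39.3 = 51.3. The longest delay here, 305 / 7 = 43.6 weeks, is not a ceiling: ethics approval (section 11.1) and re-consent come first, so contact may have been later. Visits due in spring and summer 2020 land far from 12 weeks on any ordinary reading of an approximate visit time. The real doubt is confined to 12-week forms that are modestly late.

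**2. Attrition.** Assume 20 per arm, so one person is 1/20 = 5 points. With hypothetical counts of 6/20 missed in each arm (30% v 30%), late contact reaching 4 in one arm and 1 in the other gives (6 − 4)/20 = 10% v (6 − 1)/20 = 25%. This shows what is possible, not what is likely, because the recovery counts were chosen to create an imbalance.

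**3. Integrated regulation.** Assumptions: 20 per arm, normal outcome with SD 1, no covariates, the same late share in both arms, small taken as a standardised difference d of 0.20, true d = 0.30, and 100,000 simulated trials per setting. The table gives the share of trials in which the answer to whether d reaches 0.20 differs with and without the late forms.

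| Late share | No fading | Full fading | Due to lateness |
|---|---|---|---|
| 10% | 0.098 | 0.103 | 0.005 |
| 25% | 0.159 | 0.179 | 0.020 |
| 40% | 0.210 | 0.241 | 0.031 |

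With no fading, a late form is as good as a punctual one, so that column is pure noise from dropping 2, 5 or 8 people per arm. With true d = 0, the answer still changes in about 9%, 14% and 19% of trials.

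**4. Keep or drop.** Standard error of d with n per arm = √(2/n + d²/(4n)). For n = 20 this is √(0.1 + 0.09/80) = 0.318. Keeping late forms with full fading adds a bias of 0.30p for late share p, so the root mean squared error is √(0.318² + (0.30p)²) = 0.319, 0.327 and 0.340 at 10%, 25% and 40%. Dropping them leaves 18, 15 or 12 per arm and standard errors of 0.335, 0.367 and 0.411. Keeping them is better in each setting.

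**5. What the records hold.** Sections 8.5 and 8.6 require re-consent for these contacts, and section 8.6 requires contact attempts to be logged. Late contacts can therefore be identified, and attrition can be counted by scheduled assessments missed or by final status. The late visits include no accelerometer wear, so step outcomes are untouched.

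**The case for a change.** The strongest case for a change is that attrition is the first primary outcome listed and is descriptive only, so its definition alone fixes the result. Intent to treat settles who is analysed and in which arm, not which time point a measurement represents. Blinding limits an arm-driven choice but supplies no label. Section 8.5 also speaks of follow-up assessments in general and covers women with no follow-up data at all. Moreover, the late contact includes an interview, which the ordinary schedule has only at 12 weeks, so placement under the 24-week heading does not fully settle the label. A few sentences would close the gap.

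Much of this stands as description: the plan is silent. But no stated rule gives a wrong answer. The equal-attrition hypothesis has no numerical margin, and the progression condition in section 10.2 does not use attrition. Nothing in the documents says that late forms enter the ANCOVA; the stated purpose is to learn what happened to these participants and whether they used the materials during the pandemic. Section 8.5's placement and section 8.6's reference to final questionnaires lean towards 24 weeks, and the effect hypotheses are set at 12 weeks, so a form from week 34 or later has no natural claim to be a 12-week value.

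**Conclusion.** The silence is real but is missing detail that a competent analyst fills sensibly: show scheduled assessments missed by arm with late contacts alongside, and label late forms by their actual time since randomisation. Either attrition count can be built from the records, no data are lost, and no formal decision turns on the choice. The size is 5 points of attrition per reclassified participant, and about 0.5 to 3 percentage points of added disagreement on the integrated-regulation reading. These figures rest on assumed values (20 per arm, a cut of 0.20, true d = 0.30, late shares of 10% to 40%), because the documents give no count of late contacts and no number for a small effect. For an unpowered pilot with descriptive feasibility outcomes, no change to the plan is called for.

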8.6. Additional communications with participants by phone, email/text, and in person

Study staff will ensure that participants have contact information for the research team and knows how to call after hours in the case of a question or problem.

Participants will be asked (but may decline) to provide alternative contacts to the study staff. At each study visit, participants will be asked if there have been any changes in their contact information or that of their alternative contacts.

Attempts at contact will be documented in each participants' contact log. Information discussed, provided to, or obtained from the participant will be documented in the log.

Study staff will provide basic technical troubleshooting with study devices (Fitbit monitor, app, camera) during business hours by text or phone. If necessary, we will set up one meeting per participant to replace broken or lost equipment. We will allow one other meeting for technical support of other kinds, if necessary.

Study staff will contact participants by phone, text or email the day before each appointment. If emailed or text regarding the appointment and scheduling, staff will respond. Study staff will also send generic cards at approximately 5 months in to the intervention period to remind the participants of their participation in the study and that they will be contacted to schedule another appointment at a later date.

Prior to determining that a participant is lost to follow up form, we will attempt to contact the participant at least 3 times, attempt contacting the alternative contact(s), and attempt a final contact by mail. A form documenting all mailed correspondence will be stored in the participants' file.

Participants will be notified that study staff may not respond to non-emergency contacts outside of normal business hours.

Additional contact may occur for the purposes of picking up/dropping off accelerometers or questionnaires.

Due to difficulties from COVID19 additional contact may occur for the purpose of collecting final questionnaires, interview, and collection/photography of material. The following steps will take place if we contact a subject for this purpose:

We will ask for their permission to re-consent for the purpose of collection/photography of material, questionnaires, and interview. This visit may be completed by using a teleconference call or in person.

